3.3.2.2 Eligibility Criteria

Inclusion Criteria
Infants born by vaginal or C-Section delivery at any of the participating centers, with \geq 35 weeks gestational age and judged clinically stable immediately after birth.*
Exclusion Criteria
Skin abnormality that precludes sensors placement.
Infants born at <35 weeks gestational age
Clinically unstable infants born at \geq 35 weeks **

*Clinically stable immediately after birth will be defined for the purposes of this Study as neonates not requiring neonatal resuscitation as determined by the MUHC “Neonatal Resuscitation within the Birthing Centre Working Protocol” (Appendix 3)

** Clinically unstable immediately after birth will be defined for the purposes of this study any neonate requiring interventions in accordance with MUHC MUHC “Neonatal Resuscitation within the Birthing Centre Working Protocol” (Appendix 3).

3.3.3 Study Interventions

Each newborn enrolled in the Study will be monitored simultaneously by both the standard of care (control) wired vital sign monitoring system (Infinity M540 monitor, Draeger, Germany) and the wireless monitoring system (intervention) (ANNE Arc chest sensor, SIBEL Health, Illinois, USA and Limb sensor (RAD7, Masimo) (Figure 9).

Both monitoring systems, will simultaneous record heart rate, respiratory rate, oxygen saturation, and skin temperature for the first 2h of age.

Figure 9. Monitoring systems – ECG and temperature

Figure 10. Monitoring Systems – SpO2

All materials and equipment required for the conduct of the study will be provided to the participating sites by the lead site. All research team members at all sites will be trained on the placement and removal of the wireless and wired monitoring including appropriate cleaning and disinfecting protocols. Training on the use of the BioDash system will also be provided as part of the study training at all sites.

Vital Sign Monitoring:

If a baby is born via:

1. *Vaginal Delivery:* Following normal, vaginal delivery, the wireless skin sensor monitoring system (Anne Arc & RAD7 Limb,Sibel Health Inc - Masimo) will be immediately placed on the newborn. In order to promote the standard practice of bonding between newborn and mother the standard of care wired monitoring system (Infinity Monitor, Drager) will be placed on the newborn after 10-20 min of age.
2. *C-section:* Immediately before birth, the infant will be randomized for the type of monitoring system to be applied first: a) the wireless sensors (Anne Arc & RAD7 Limb,Sibel Health Inc - Masimo) or b) standard of care wired system (Infinity Monitor, Drager). In order to promote the standard practice of bonding between newborn and mother the second monitoring system will be placed on the newborn after 10-20 min of age.

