1.1 Background

Globally, around 140 million infants are born every year, representing 4 births/second every day. Of these, approximately 10 million infants do not breathe immediately after birth, and 60% require basic neonatal resuscitation.^{1,2} The International Liaison Committee on Resuscitation (ILCOR) publishes a consensus on newborn resuscitation science every 5 years and currently recommends monitoring of oxygen saturation (SpO₂), heart rate (HR; monitored by electrocardiography), and skin temperature (T_{skin}) during neonatal resuscitation.³ Therefore, in the delivery room, the use of expensive and large base monitoring units attached to a power supply is usually necessary. To obtain the signals, wired skin sensors and electrodes are placed on the patient. Altogether, these are barriers for adoption of the ILCOR recommendations due to the lack of portability and the training required for their use in environments with low resources and high number of deliveries.⁹ Indeed, many delivery centers in low and middle income countries (LMIC) either do not monitor or use a variety of different systems whose accuracy and safety is unknown (**Figure 1**). The Argentine Pediatrics Society, after evaluating the causes of neonatal deaths of hospitalized newborns, reported that, at the time of death, many newborns were not adequately monitored, concluding that lack of adequate neonatal vital sign monitoring may contribute to an increase in preventable newborn unexpected catastrophic events leading to death.¹⁰ Furthermore, the necessary equipment is usually in the same room of the mother, demanding close communication within teams and with the family. However, delivery room (DR) technologies should facilitate, rather than impede, family integration and early bonding. Additionally, infants are born with wet skin and a transitioning cardiorespiratory system, but existing monitoring solutions were not primarily designed for resuscitation and may also have a significant delay (up to 1 minute) before displaying data, which can affect critical clinical decisions. As knowledge about the process involving the transition from fetal to neonatal life increases, it is expected that more technologies will evolve for use in the DR. These technologies should be developed for use where the greatest burden of morbidity and mortality exists (LMIC) to have the largest impact in neonatal health care.^{1,2}

[figure not shown]

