Ongoing work includes the analysis of RR, SpO₂ and T_{skin} signals to evaluate the overall feasibility, reliability, and accuracy of ANNE® One sensors.

[figure not shown]

Figure 3. Cumulative histograms of HR recorded with a wired (blue) and a wireless system (red) for a typical subject

Additionally, we developed methods to synchronize and align all signals acquired from the wired and wireless monitors to allow sample-to-sample comparison.³³ (**Figure 4**).

[figure not shown]

Figure 4. The sample signals following pre-processing, where: (A) the short gap was filled, (B) aligned features share a common time due to resampling, (C) the initial delay was removed, and (D) the signals remain aligned 6 hours later due to drift correction.

More recently, the feasibility of this wireless system was evaluated by correlating periods of missing data in HR with automatically generated alert signals and manually recorded annotations. (**Figure 5**). Gaps in the wireless HR signals were most often linked to Bluetooth disconnections and KMC. Current work is examining the roles of: (1) movement artifact, (2) signal to-noise ratio, as a means to understand problems and improve the feasibility of using a wireless system in the NICU. ³⁴

[figure not shown]

Figure 5. Group results from HR gap classification pertaining to: (A) the correlation of gaps in the wireless system with alert flags, and (B) the correlation of gaps in both the wireless and wired systems with the seven-most prominent comment codes. HR sample coverage = 86%.

Based on these results and on interviews conducted with parents and NICU nurses, Sibel made important modifications to the ANNE One® chest sensor, including its size, shape (configuration), position of the antenna, and type of skin adhesive. The new sensor called ANNE Arc® is now available, has been approved by Health Canada for research (ITA), and will be used in this Study along with the RAD7 Limb Sensor (**Figure 6, Figure 7**). Moreover, a large international survey on the use of wired and wireless technology in the NICU was circulated to HCPs all over the world. Almost 1000 HCPs have replied, and analysis is underway. Finally, in collaboration with researchers at Northwestern University, a wireless acoustic device for

monitoring airflow, breathing efforts and bowel sounds was developed and tested. Results were presented at the PAS meeting in May 2023, and the manuscript was accepted for publication in *Nature Medicine*.³⁵

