2.2 Aims

Healthcare technology assessment is the multidisciplinary evaluation of medical technologies with regard to **feasibility, safety, efficacy**, indications for use, cost, and cost-effectiveness. A complete assessment should explore the scientific, ethical, economic, and social reasons for adopting a technology and it may influence the quality of service and distribution of resources.

In this multicenter study, we aim to assess the first 3 important criteria.

Aim 1 – To determine the **feasibility** of using a wireless system immediately after delivery and for the first 2h of age, while in the obstetrical center under unsupervised parents' care. The following outcomes will be measured for both wired and wireless systems:

- a. Percentage of time for which HR, RR, SpO₂ and T_{skin} data are displayed.
- b. Occurrence of gaps in signal detection/recordings (% and length).
- c. Causes of the gaps in signal detection/recordings.
- d. Descriptive analysis of user surveys and their satisfaction with the wireless system.

Aim 2 - To investigate the **safety** of using this wireless system immediately after delivery and for the first 2h of age. The following outcomes will be measured for both wired and wireless systems:

- a. Skin score to be determined by a blinded dermatologist using de-identified pictures of the skin after removal of the sensors of each system.
- b. Pain scale to assess any discomfort or pain during the removal of the sensors.
- c. Clinically significant events detected by the wired system (HR < 100 bpm or SpO₂ < 80%) but missed by the wireless system.

Aim 3 – To assess the **accuracy** of this wireless system in measuring HR, RR, SpO₂ and T_{skin} signals compared with the “standard of care” wired system. The following outcomes will be computed:

- a. Correlation coefficient
- b. Slope
- c. Variance accounted for
- d. Bias

Further subgroup analyses will be conducted to assess for systematic differences in feasibility, safety, and accuracy of the wireless system between the following:

- High vs. Low and Middle income countries
- Female vs. Male subjects
- Term vs. Preterm (born < 37 weeks gestational age) infants
- C-section vs. Vaginal delivery

- Skin pigmentation

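### The planned C-section vs vaginal comparison of wireless feasibility is partly confounded with sensor placement order, and the available text sets no window for coverage and gaps

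*Combined protocol and SAP*

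**What the plan says.** Section 3.3.3 gives the recording period as common to both systems: "Both monitoring systems, will simultaneous record heart rate, respiratory rate, oxygen saturation, and skin temperature for the first 2h of age". The same section then staggers placement. In vaginal births the wireless system goes on at once and the "standard of care wired monitoring system (Infinity Monitor, Drager) will be placed on the newborn after 10-20 min of age". In C-sections, "Immediately before birth, the infant will be randomized for the type of monitoring system to be applied first", and the second system follows after the same 10-20 min. No allocation ratio is given.

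Section 2.2 lists the Aim 1 outcomes for both systems. They include the percentage of time each signal is displayed and a gap outcome worded "Occurrence of gaps in signal detection/recordings (% and length". Neither has a start time, an end time or a denominator. The section also plans subgroup analyses for "systematic differences in feasibility, safety, and accuracy of the wireless system between the following", one of which is "C-section vs. Vaginal delivery".

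Section 4 uses phase 1a coverage for the sample size. Its analytical approach covers descriptive demographics and the accuracy measures only: there is no coverage or gap analysis and no mention of order. Appendix 1 (item 3) records the order of monitoring.

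Figure 8 (the study design illustration) and the text between sections 3.2 and 3.3.2 were not available, so a window could be shown there.

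**The concern.** Vaginal birth fixes the order as wireless-first, while C-section mixes the two orders. A simple comparison of wireless coverage or gaps between delivery modes therefore also compares a group that is entirely wireless-first with one that is only partly so. Whatever order does to coverage will appear as a delivery-mode difference.

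What order does depends on the unstated window:

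- **Window of 0-120 min of age.** The later system is charged for minutes in which it was not on the infant.
- **Device-on time.** That charge disappears, but only the first-placed system is scored in the minutes just after birth, which section 1.1 describes as a time of wet skin and cardiorespiratory transition.

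The same ambiguity affects the wired vs wireless contrast in vaginal births, where order never varies and an order effect cannot be estimated. What is at stake is the interpretation of reported results. The plan attaches no test or threshold to these comparisons.

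**Working it through.** **Inputs.** Phase 1a coverage (section 4): HR 98.7 ± 2.2% wired and 85.3 ± 14.3% wireless; SpO2 93.9 ± 6.3% wired and 66.5 ± 20.8% wireless. Delay to the second system: d = 10 to 20 min (section 3.3.3). Nominal period: 120 min. Assumptions: 1:1 order in C-sections, and phase 1a coverage applying while a system is on. Phase 1a was in a NICU and used the earlier chest sensor.

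**1. The plan's own coverage figure, for scale.** Section 4 gives 2.7 points for HR coverage. (1.960 + 1.282) × √(2.2² + 14.3²) / √300 = 3.242 × 14.47 / 17.32 = 2.71. It reproduces if the 600 infants are treated as two groups of 300. It concerns wired vs wireless and is not a threshold for delivery mode. The SpO2 figure of 3.46 does not reproduce by this formula (4.07), but nothing here rests on it.

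**2. Window loss on 0-120 min.** d/120 = 10/120 = 8.3% to 20/120 = 16.7% for the later system.

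**3. Delivery-mode comparison, order alone, on 0-120 min.** Half the C-section infants are wireless-second and lose d/120 of their wireless coverage; no vaginal infant does. The apparent deficit in C-sections is coverage × (d/120) / 2:

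- HR: 85.3 × (10/120)/2 = 3.6; 85.3 × (20/120)/2 = 7.1 points.
- SpO2: 66.5 × (10/120)/2 = 2.8; 66.5 × (20/120)/2 = 5.5 points.

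**4. Wired vs wireless in vaginal births on 0-120 min.** Wireless minus wired = wireless − wired × (120 − d)/120:

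| Signal | Device-on | d = 10 | d = 20 |
|---|---|---|---|
| HR | 85.3 − 98.7 = −13.4 | 85.3 − 90.5 = −5.2 | 85.3 − 82.25 = +3.05 |
| SpO2 | 66.5 − 93.9 = −27.4 | 66.5 − 86.1 = −19.6 | 66.5 − 78.25 = −11.75 |

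**5. Wired vs wireless within C-sections on 0-120 min.** With 1:1 order the losses nearly cancel. The mean HR contrast is −12.8 (d = 10) or −12.3 (d = 20) against −13.4, a shift of 0.6 to 1.1 points. For SpO2 it is −26.3 or −25.1 against −27.4, a shift of 1.1 to 2.3 points.

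**6. Device-on time.** The losses in steps 2 to 5 are zero. The remaining effect is that only the first-placed system is scored in the early minutes. The documents give no early coverage, so its size is unknown. If early capture is poor, it would lower wireless coverage in vaginal births, the opposite direction from step 3. For scale only: each minute without display costs the first-placed system 1/120 = 0.83 point, and section 1.1 says existing monitors "may also have a significant delay (up to 1 minute) before displaying data".

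**7. Precision if the delivery-mode contrast is limited to wireless-first infants.** 95% half-width = 1.96 × 14.3 × √(1/nV + 1/nC), with 600 infants and half the C-section infants kept. The C-section share is not given, so a range is shown:

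| C-section share | nV | nC, all → wireless-first | Half-width, all → wireless-first |
|---|---|---|---|
| 20% | 480 | 120 → 60 | 2.9 → 3.8 |
| 40% | 360 | 240 → 120 | 2.3 → 3.0 |
| 60% | 240 | 360 → 180 | 2.3 → 2.8 |

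**The case against.** The strongest reply is that every quantified shift needs a 0-120 min denominator, and the plan nowhere says it will count time before a sensor is attached as missing. Device-on or overlap time is at least as natural. Section 1.3 describes methods in phase 1a to "synchronize and align all signals acquired from the wired and wireless monitors to allow sample-to-sample comparison", and section 3.3.4 times display from application of the leads. This stands: the missing window is an ambiguity, not a demonstrated error. Alignment of signals does not itself define a coverage window, however, and the wording about the first 2 h of age leaves the other reading open.

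A reader might infer that the wired vs wireless HR result will change sign. The documents do not support resting the point on that. It needs the 0-120 min denominator, phase 1a coverage, and wired placement later than 120 × (1 − 85.3/98.7) = 16.3 min. At 15 min the contrast is still 85.3 − 86.4 = −1.1. For SpO2 the crossing is at 120 × (1 − 66.5/93.9) = 35.0 min, outside the permitted range.

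A reader might also infer that delivery mode and order are fully confounded. They are not: C-section infants randomised to wireless-first share the vaginal order, and order is recorded. It is also fair that this is one of five further subgroup comparisons with no test attached. None of this answers the central point, that the comparison as planned pools orders and the analysis text makes no use of order.

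**Conclusion.** The concern holds in a limited form and should be fixed. On the available text, the delivery-mode comparison of wireless feasibility is partly confounded with placement order under either reading of the window. With a 0-120 min window the artefact is 3.6-7.1 points for HR and 2.8-5.5 for SpO2, given 1:1 order and phase 1a coverage. With device-on time its size cannot be derived from the documents. The 8.3-16.7% window loss for the later system depends only on the 10-20 min delay and the 0-120 min denominator, not on phase 1a.

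No stated decision changes, so the harm is to interpretation. The reason to act is that the trial already randomises order in C-sections and records it, so the confounder can be removed almost for free. Confidence is medium, because Figure 8 or the unavailable text might define a window.

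**What to change.** 1. **Delivery mode.** Report wireless feasibility by placement order and do not pool orders. The like-for-like contrast is wireless-first C-section vs vaginal infants. Because order is randomised in C-sections, the wireless-first infants are a random subset of them, so the cost is precision only: for HR coverage, the half-width rises from 2.9 to 3.8 points at a 20% C-section share.
2. **Paired coverage and gaps.** Compute them per infant and per signal over a common window, from placement of the later system to 2 h of age or earlier stop. Time before placement is not a gap, and a system that never displays a signal counts as 0%. Report time to first display beside coverage. Do not start the window at first display: it would then depend on the outcome and drop slow start-up from coverage. A sensor first displaying at 115 min would be scored over only 5 min. The price is that a 1-min start-up delay costs the second system 1/110 to 1/100, about 0.9-1.0 point.
3. **Early period.** The common window covers only about 100-110 min and omits the minutes just after birth that Aim 1 names. Report the first-placed system's coverage before overlap separately, by delivery mode and order. Compare systems in that period only in C-section infants, by randomised first system.
4. **Wording and form.** Reconcile the simultaneous-recording statement in section 3.3.3 with the staggered placement. Make sure the data form records the placement clock time of each system: the monitor-time rows in the Comments Log (Appendix 1, item 5) may be only monitor clock readings, and the stopwatch in section 3.3.4 gives a duration.

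Items 1 to 3 are analysis text. Item 4 may add one field per system to the form. No placement procedure changes.

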3.3.4 Data Collection

The Study research team at each site will collect standard demographic and clinical information from mothers and newborns as described in the Data Collection Form (see Appendix 1) during the 2hrs of vital sign recording (see Figure 11 below). With a stopwatch, a designated trained research team member(s) will time the recording as the period (sec.) that elapses from the application of the leads until the first display of data on the monitors, for all the sensors of both systems. Data will be continuously recorded while the mother/caregiver provides routine care. Annotations as described in the Data Collection Form will be documented by the research team regarding movements, breast-feeding attempts, cleaning/drying, patting, etc. (see Appendix 1). The vital signs data displayed on the monitors will only be visible to designated research team member(s), and all alarms will be turned off so as not to disturb parents and newborn. Any clinically relevant changes observed in vital sign parameters will be communicated by the research team member(s) to the obstetrical/neonatal team. A clinically relevant event is defined as follows: HR < 100 bpm or SpO₂ <85% (after the first 10 minutes of life) with sinusoidal wave as detected on either monitoring system during the course of the 2hr continuous monitoring. If the neonate requires any intervention to reverse instability, such as oxygen therapy and ventilator support, data collection will end but the data collected up to that time point will be included. The participating baby will not be withdrawn from the study.

The following data will be collected:

- Skin assessment:* In order to assess the safety of the wireless skin sensors, photographs of the infant's skin will be taken before device placement and after device removal. Each participating site will send de-identified digital photos coded (with the participant's study code) to the dermatologist for blinded assessment using the skin score (Neonatal Skin Condition Score - NSCS) as described in the Data Collection Form.
 - **Neonatal Skin Condition Score (NSCS)³⁷:** Photographs of the infant's skin at the site of device placement for both the chest and limb skin sensors will be taken prior to device

placement and following device removal. These photographs will then be scored by a dermatologist using the NSCS. Scores range from 3 (intact skin condition) to 9 (very poor skin condition).

- Skin Pigment: Previous research has highlighted the challenges of some pulse oximeters in providing accurate readings for skin with darker pigmentation and as a result has emphasized the need to investigate the performance of pulse oximeters for different skin tones^{38,39}. The infant's skin color will be recorded using the adapted Munsell System Soil Color Chart (2009 Revision, Munsell Color, Grand Rapids, Michigan), Hue7.5YR to investigate impact of skin pigmentation on pulse oximetry accuracy. This scale has previously been used in research on neonates⁴⁰.
- *Pain Assessment*: As well, neonatal pain will be assessed throughout the sensor removal process. The pain scale (NIPS) will be completed by the study team member at the time of sensor removal and entered into REDCAP.
 - Neonatal Infant Pain Scale (NIPS)³⁶ : At the time of device removal, the researcher will complete the NIPS to ensure removal of adhesive does not cause significant discomfort to the patient. The scale consists of 6 items. Scores range from 0 to 7, with scores greater than 3 indicating presence of pain. This scale has been widely validated for the assessment of acute pain in neonates. This scale will be included in the Data Collection Form.
- *Surveys*: In order to assess feasibility on the use of wireless sensors to monitor babies after birth, a survey will be conducted to get the opinions of parents and Health Care Professionals involved in the care of the baby and mother. The survey will be presented in hard copy form as well as through REDCAP.
 - Parent Survey: Parents of the participating infant will be asked to complete a short survey to after the sensors of both systems are removed. The survey will be coded with the study code assigned to the participating infant, no personal health information or personal information will be asked of the parent for the completion of the survey. (See Appendix 2).
 - Health Care Professional Survey: HCPs involved in the care of the infant and mother after birth will be asked to complete a short survey after the sensors of both systems are removed in order to assess how the HCPs felt about the wireless skin sensors as compared to their experience of the standard of care wired monitoring system. (See Appendix 2).

REDCAP

Clinical data, images, information as described in the Data Collection Form (Appendix 1) and Survey (Appendix 2) responses will be entered into a REDCAP database hosted at the RI-MUHC through the CORD platform. A service agreement has been entered into with CORD and the Principal Investigator for the REDCAP database set up and support for the study's data management. Each participating site will be provided access to the study REDCAP database at the RI-MUHC and be responsible for entering their site's

data into REDCAP. Participating sites will be expected to sign a site user agreement before permitting access to REDCAP. The HCP and parents will be provided a link to the survey in REDCAP or a hard copy depending on their preference and/or the preference of each participating site. The sites will be asked to send their a copy of each completed Data Collection Form and a hard copy of the survey in order to query and ensure compliance and consistency in the conduct of data collection and data entry on a monthly basis. No site will be able to access another site's individual site data and will only have access to REDCAP for their site. The de-identified study database will only be accessible to the lead site and all analysis of the study data collected in REDCAP will be done by RI-MUHC study team members. Results will be shared with the participating sites on an ongoing basis for training purposes as well as to support the drafting and submission of manuscripts, abstracts, and presentations as the study progresses.

BIODASH

The research team will use the data collection software system called Biosensors Data Aggregation and Synchronization (BioDASH) developed by the Smart Hospital Project team in collaboration with iKinesia Inc. (Montreal, CANADA) to stream, visualize, and log data all in real-time from the standard of care wired monitoring system and the wireless monitoring system into a single study laptop (Figure 10) . Data from all monitoring devices will be aggregated and synchronized for display and logged into files for eventual offline analysis. See Figure 10 below for the BioDASH high-level system architecture and components. The BioDASH application is designed not to interfere with the patient monitor and will not store any protected health information. The streamed data logged by the application will be stored locally on the study laptop until the end of the recording period when it will be uploaded to a secure DropBox™ professional account created for the study by the Principal Investigator as well as a hard drive which will be kept in a locked cabinet in a room to which only RI-MUHC study personnel will be granted access. The data from all sites captured by BioDash will be uploaded to the secure DropBox™ professional account created for the study as well as a hard drive which will be kept in a locked cabinet in a room to which only study personnel will be granted access. The BioDash system as well as all the required devices will be provided to all participating sites by the Principal Investigator. All participating site study personnel will receive training on proper

placement of the sensors and wires, all data capturing systems and proper study conduct by the Principal Investigator and designated lead site study personnel.

[figure not shown]

Figure 11. BioDASH system architecture and components

[figure not shown]

Figure 12. Data obtained from each monitoring system will be de-identified and on a secure local server and then to a cloud before it is downloaded onto a secure data repository at the RI-MUCH for investigators' assessment.

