5. COMMENTS LOG

Comments	0 (Baseline)	1	2	3	4	5	6	7	8
Time wired Monitor									
Time wireless Monitor									
Location of newborn (k = kangaroo care, b = in bed)									
Time (clock)									
Position of newborn (s = supine, p = prone, side line =sl)									
Time (clock)									

Muscle tone (normal = n, hypotonic = hypo, hypertonic = hyper)								
Time (clock)								
Quality of reading (N/A = no issue, A = presence of artifact, P = poor signal capture)								
Time (clock)								
Interventions performed during recording (N/intervention)								
Time (clock)								
Sensor disconnection (N/reason*)								

6. COMMENTS LOG – CODE WORDS (for redcap)

Event	Drop-Down Code	Details
Kangaroo Care = KC	KC start	Start of kangaroo care
	KC end	End of kangaroo care
Nursing Care = NC	NC check	Quick nurse check (may open incubator, no real manipulation of infant)
	NC start	Routine care, that is longer than quick check, includes diaper change, feeding, etc)
	NC end	End of routine care procedures
Parent Care = PC	PC start	Holding baby, changing diaper, umbilicus care, bath time
	PC end	End of parent care procedures
Breastfeeding = BF	BF start	Start of breastfeeding
	BF end	End of breastfeeding
Repositioning = R	R supine	Baby repositioned to supine
	R prone	Baby repositioned to prone
	R Side	Baby repositioned to side
	E end	Exam end

xEvent Other	EO [specify]	Other relevant event not accounted for by annotations list please specify
Sensors (both) = S	SR start	Sensors removed for
	SR end	Sensors placed back
Chest Sensor = C	CR start	Chest sensor removed for exam
	CR end	Exam over chest sensor placed back on
	CA	Chest sensor readjustment
Limb Sensor = L	LR start	Limb sensor removed
	LR end	Limb sensor back on
	LA	Limb sensor readjustment
	LX	Limb sensor falling off [ES1]
	LH right	Limb location change – now on right hand
	LH left	Limb location change – now on left hand
	LF right	Limb location change – now on right foot
	LF left	Limb location change – now on left foot
Drager Electrodes = E	ER start	Electrodes removed
	ER end	Electrodes back on
	EA	Electrodes readjusted/moved
Massimo Oximeter = O	OR start	Oximeter removed
	OR end	Oximeter back on
	OA	Oximeter readjusted
	OH	Oximeter moved to hand
	OF	Oximeter moved to foot
Temperature and Humidity	T() H()	Temperature and humidity recording

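### The skin-pigmentation analysis can test whether wireless–wired SpO₂ agreement varies with pigmentation, but not whether either oximeter is accurate on darker skin; section 3.3.4 says more than the design can deliver

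*Combined protocol and SAP*

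**What the plan says.** - **Purpose of the pigment measurement (3.3.4, Skin Pigment).** The protocol cites earlier work on "the challenges of some pulse oximeters in providing accurate readings for skin with darker pigmentation" and then says Munsell colour is recorded "to investigate impact of skin pigmentation on pulse oximetry accuracy".
- **Subgroups (2.2).** "Further subgroup analyses will be conducted to assess for systematic differences in feasibility, safety, and accuracy of the wireless system"; skin pigmentation is the last factor listed.
- **What accuracy means (2.2, Aim 3).** HR, RR, SpO₂ and skin temperature from the wireless system are assessed "compared with the “standard of care” wired system".
- **Accuracy measures (section 4).** Correlation, slope, variance accounted for and Bland-Altman bias, all computed between the two systems. Section 4 says nothing about how the subgroup results will be analysed or interpreted.
- **Source of the saturation readings (3.3.3).** "Both monitoring systems, will simultaneous record heart rate, respiratory rate, oxygen saturation, and skin temperature". The monitoring log in Appendix 1 has one wired and one wireless SpO₂ row and no other saturation measurement.
- **Devices.** Section 3.3.3 gives the wireless saturation sensor as "Limb sensor (RAD7, Masimo" and names the wired system only as the Draeger monitor. The comment codes in Appendix 1 list "Massimo Oximeter = O" separately from the wireless limb sensor and next to the Draeger electrodes.

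**The concern.** The protocol raises a doubt about pulse oximeters on darker skin and then uses one pulse oximeter as the yardstick for another. A reference that may carry the error under study cannot reveal that error where both devices have it. If the two sensors misread darker skin to a similar degree, their difference would look the same in light and dark skin, and the analysis would find no pigmentation effect.

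What is at stake is the conclusion. The protocol hopes for wide adoption in low- and middle-income countries. As 3.3.4 is worded, a null subgroup result could be reported as evidence that pigmentation does not affect oximetry accuracy. The design does not support that statement, and no passage limits the result to agreement between devices.

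**Working it through.** **1. The plan's own figure.** Section 4 gives an expected margin of error of 0.26% for SpO₂ bias, from a phase 1a SD of 1.4%, two-sided alpha 0.05, power 0.9, n = 600 and 4% drop-out.

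- Analysable infants: 600 × 0.96 = 576.
- Formula that fits: SD × (z₀.₉₇₅ + z₀.₉₀) × √(2/576) = 1.4 × 3.2415 × 0.05893 = 0.267.
- SDs that round to 1.4 (1.35 to 1.45) give 0.258 to 0.277, so 0.26 is reproduced within rounding.

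This precision refers to the wireless–wired difference, that is, to agreement between two oximeters.

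**2. What that difference contains.** For one infant let T be true saturation, S the pigment error common to both devices, and E_wl and E_w the error specific to the wireless and the wired device.

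- Wireless reading = T + S + E_wl; wired reading = T + S + E_w.
- d = wireless − wired = E_wl − E_w.

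T and S both drop out. The dark-minus-light contrast in d is the wireless pigment error minus the wired pigment error, whatever the sample size. Correlation, slope and variance accounted for use the same two readings and bring in no third one, so they cannot recover S either.

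**3. What a result could mean.** These values, in SpO₂ points, are for illustration only:

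| Wireless pigment error | Wired pigment error | Contrast in d |
|---|---|---|
| 0 | 0 | 0 |
| 3 | 3 | 0 |
| 2 | 0 | +2 |
| 0 | −2 | +2 |
| 3 | 1 | +2 |

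A zero contrast fits two accurate devices or two equally wrong ones. A contrast of +2 fits an error in the wireless device, in the wired device, or in both.

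**4. What the design can detect.** Assume that half the infants are darker-skinned (288 and 288) and that the SD of d is 1.4, the value from phase 1a in the NICU.

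- Detectable contrast in d: 1.4 × 3.2415 × √(2/288) = 0.38 points at 90% power.
- Simulation under the same assumptions (576 infants, 2,000 runs per setting):

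| Shared error in darker skin (points) | No wireless-only error: mean contrast | Rejected | 0.5-point wireless-only error: rejected |
|---|---|---|---|
| 0 | 0.004 | 6.2% | 98.8% |
| 1 | −0.002 | 4.8% | 98.9% |
| 2 | −0.006 | 5.3% | 99.2% |
| 3 | 0.000 | 5.0% | 98.4% |
| 5 | −0.004 | 5.0% | 98.9% |

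Shared error from 0 to 5 points leaves the contrast at about zero and rejection at about the nominal 5%. An extra 0.5 points in the wireless sensor alone is found almost every time. The 0 to 5 range is an assumption; the documents give no figure.

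**5. Is there any other reference?** The aims, the data collection section, the data collection form and section 4 mention no arterial saturation, blood gas or co-oximetry.

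**The case against.** The strongest reply is that the plan defines its terms. Aim 3 says openly that accuracy is relative to the wired system, section 3.1 describes the same comparison, and the pigmentation subgroup inherits that definition. On this reading the phrase in 3.3.4 is only a reason for recording skin colour, and the analysis is already the narrower one. This stands in part: the comparator is disclosed. But 3.3.4 speaks of pulse oximetry accuracy in general, directly after doubting oximeters on darker skin, and nothing in the plan ties the pigment result back to agreement.

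A second reply is that the analysis is useful as designed. That stands. Pigment error that differs between the devices is detectable with good power under the assumptions above, and the subgroup also covers feasibility and safety.

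A reader might go further and infer any of the following, none of which the documents support:

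- **Both oximeters over-read on darker skin by a known amount, most of it hidden.** The documents give neither the size of any pigment error nor the shared fraction. A percentage hidden would simply repeat whatever fraction was assumed.
- **The two sensors share their error because both are Masimo.** The wired probe's make is inferred from a comment code that does not say wired, and the SpO₂ figure is not shown in the copy reviewed. A common brand makes shared error plausible; it does not establish the same sensor, algorithm or error.
- **A null result will be misread.** No passage says how a null will be interpreted, so this is a foreseeable risk only.

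**Conclusion.** The point holds as a mismatch between stated purpose and design. For SpO₂, the pigmentation analysis estimates whether agreement between two oximeters varies with skin colour. It cannot estimate the effect of pigmentation on the accuracy of either one, and enlarging the sample would not change that. A null result is compatible with equal error in both devices, and a non-null result does not identify the device at fault.

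The cancellation is algebraic and rests on one fact from the documents: the only reference for saturation is another skin-sensor SpO₂ reading. It does not depend on the brand of the wired probe. The simulation rests on equal subgroups, an SD of 1.4 and assumed shared errors, and only illustrates the algebra. No size is claimed for the shared error. Sample size, data and planned statistics are unaffected; the sentence the trial may write at the end is what changes.

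**What to change.** 1. In 3.3.4 (Skin Pigment) and in the pigmentation subgroup as it applies to Aim 3, restate the SpO₂ objective as: *whether wireless–wired SpO₂ agreement varies with skin pigmentation*.
2. In section 4, add: *A null result does not show that either oximeter is accurate on darker skin, and a non-null result does not show which device is in error.*

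The cost is a few lines of text and a narrower claim. Data collection, sample size, procedures and planned statistics stay the same, and no arterial sampling is asked for.
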